2 BACKGROUND

2.1 Disease Background

Head and neck cancer (HNC) is the 6th most common cancer, accounting for an estimated 650,000 newly diagnosed cancers each year worldwide [1]. The advent of concurrent chemoradiotherapy (CRT) led to an excellent 5-year cancer free survival of >70% [2, 3]. However, normal tissues are inevitably exposed to high radiotherapy doses leading to a range of acute and late treatment toxicities.

Swallowing dysfunction (dysphagia), primarily due to fibrotic stricturing at the pharyngo-oesophageal junction (POJ), often in conjunction with nerve and muscle damage, is the most common and the most devastating [4, 5] of the long-term complications in survivors. Fibrosis is a common consequence of RT in many organs. Post-RT strictures of the pharyngoesophageal junction (POJ) have an incidence of 20% in radiographic studies[6]. However, in our cohort (n=35) of HNC patients with dysphagia (approx. 60% of all our HNC survivors[7]) who underwent empiric dilatation, 80% had reduced POJ compliance on direct measurement at endoscopy[8]. Hence, the true prevalence of reduced POJ compliance contributing to dysphagia is approximately 45% of all HNC survivors. Traditionally, stricturing was believed to be a delayed complication.

Pentoxifylline (PTX) is currently used to improve circulation in peripheral vascular disease. Although its exact mechanism of action as an anti-fibrotic agent has not been fully elucidated, in-vivo, it has been shown to increase red blood cell flexibility, dilate blood vessels and inhibit inflammatory reactions. In-vitro studies have indicated that Pentoxifylline inhibits cells that synthesize the structural framework of animal tissues and increase activity of enzymes which break down collagen [9].

The role of Vit E as a scavenger of the reactive oxygen species generated during oxidative stress protecting membrane lipid components is well documented [10]. In addition to its antioxidant properties, many of Vit E activities are mediated by a non-antioxidant mechanism involving regulation of genes known to be involved in fibrotic process[10].

Interestingly, Pentoxifylline and Vit E display drug synergy with the effect of the combination being more potent than that of either of the individual treatments, even at much higher concentrations[11]. Pentoxifylline combined with Vit E has been demonstrated in both in-vitro and animal studies[12] as well as clinical studies[11] to reverse chronic RT-induced fibrosis. Several controlled and uncontrolled trials in women with breast cancer after RT demonstrated reversal of RT-induced fibrosis in the treated group [13-15]. In HNC, data is also encouraging but currently limited to uncontrolled studies. In one study, Pentoxifylline alone achieved reversal of painful iscarring in 4/6 patients[16]. In a larger cohort, an objective response to treatment

at 12 months was recorded in 23/28 (83%) RT-induced fibrosis areas, with a mean decrease of 67% in their surface areas [12].

2.2 Rationale for performing study

Strictures of the POJ, are traditionally managed by endoscopic dilatation imposing a significant burden on patients and the healthcare budgets as it requires sedation, operating theatre staff and multiple dilatation sessions. While the response rate is good (75%) it is not durable with a relapse rate of 50% at 19 months. Multiple sessions are often required, firstly to achieve a safe and satisfactory response and secondly to maintain remission. In a review of 54 consecutive patients in our department, 203 dilatations were required over 5yrs (average of 4 per person). With this ongoing burden of maintenance therapy, there is an urgent need for a safe but more effective and durable method to manage this problem.

Up to date there is a paucity of proven anti-fibrotic pharmacological approaches. Pentoxifylline (PTX) and Vitamin E (Vit E) combination, which is today available for clinical use, shows promising results and may be clinically useful in the management of established POJ strictures currently managed by endoscopic dilatation, however, this efficacy needs to be established in a rigorous RCT

3 AIMS AND HYPOTHESES

This is preliminary pilot study, conducted in order to evaluate feasibility, time, cost, and effect size, and consequently provide information to predict an appropriate sample size and improve the study design prior to developing a full scale randomised controlled trial (RCT).

The specific aims of the full scale RCT are study is to determine whether combination of Pentoxifylline and Vitamin E prevent symptom relapse and improve compliance of pharyngoesophageal junction after endoscopic dilatation.

Primary Hypothesis: Patients treated with Pentoxifylline and Vitamin E have a more compliant POJ, 12 months after endoscopic dilatation when compared with placebo treatment.

Secondary Hypothesis: Following endoscopic dilatation of POJ, the dysphagia relapse rate is reduced in patients treated with Pentoxifylline and Vitamin E compared with placebo.

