4.5 Number of participants

40 participants (20 per group)

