6.2 Study Plan

Following informed consent, but prior to randomisation, participants will undergo a baseline diagnostic endoscopy as per 'standard of care'. While sedated the compliance (elasticity) of their pharynx will be assessed using EndoFLIP (see 6.3.2 below) and they will undergo an endoscopic dilatation procedure. If baseline compliance of the POJ is reduced ie: a fibrotic stricture is present, the EndoFLIP assessment will be repeated after dilatation and participants will be randomised to receive either 1) PTX + VitE or 2) Placebo after the dilatation. Endoscopy and dilatation is part of routine care and is indicated regardless whether a patient is participating in the study.

NOTE: In case when dilatation endpoint is not met during the first dilatation (see 6.3.3 below), endoscopy will be repeated until one of the endpoints is met and then post-dilatation EndoFLIP assessment will be performed and participant will be randomized and commence study medication. Repeated incremental dilatation are part of routine care (see 6.3.3 below).

Following discharge, patients will be followed-up by a monthly phone call while on study medication for 3 months (see telephone script in appendix). From 3 to 12 months participants will have the option to attend a 'Swallow clinic' every 3 months where they will return unused medication and their swallowing function will be assessed by SSQ. Otherwise medication and SSQs will be returned by posting ad reply-paid envelopes to the participants.

Repeat endoscopy with EndoFLIP will be performed at 12 months to assess the change in POJ compliance from the immediate post-dilatation assessment.

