7 RANDOMIZATION AND BLINDING

Patients will be randomised during the first endoscopic session following stricture confirmation and endoscopic dilatation (screened and consented prior).

- Ratio 1:1
- blocked randomization with random block sizes

- stratified by 1) treatment naive and 2) previous dilatation(s). Established strictures, which have been dilated previously, may behave differently to those undergoing index dilatation

To ensure double blinding is maintained, blinding of the study medication and dispensing will be managed by Clinical Trials Senior Pharmacist at the hospital pharmacy independent of the study team.

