8 STATISTICAL CONSIDERATIONS

8.1 Sample Size Calculation

The sample size of 40 patients for this pilot is based on the number of patients we estimate to recruit over the course of 12 months and maintain the study within budget.

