8.2 Statistical Analysis Plan

This is a pilot study aiming to evaluate the feasibility of a full-scale project as such we will assess the following:

- 1) Exclusion/enrolment rates
- 2) Withdrawal rate
- 3) Tolerance to trial medication
- 4) Compliance to therapy
- 5) Data integrity
- 6) Protocol violations and trial completion rate
- 7) Dilatations required
- 8) Adverse Events

Treatment efficacy will be evaluated however the goal is to estimate the trajectory of change of the two continuous outcome variables (SSQ and Pharyngeal Compliance) within subjects from immediately post-dilatation out to 12months. These estimates will help to determine required sample size to show clinically relevant effect and design a full-sized trial competitive for Cat 1 funding.

Outcome measures

Primary: Dysphagia symptom severity - assessed by SSQ (see above) at baseline before dilatation and every 3 months.

Secondary: Pharyngeal compliance assessed by EndoFLIP at 12 months (see above);

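### The full trial should be sized on a stated between-arm difference, with the pilot supplying the SD and feasibility rates but not the effect size

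*Protocol*

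**What the plan says.** Section 3 describes a pilot meant to "evaluate feasibility, time, cost, and effect size, and consequently provide information to predict an appropriate sample size". Effect size is thus one of the named inputs to sizing.

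Section 8.2 lists eight feasibility measures and then turns to efficacy: "the goal is to estimate the trajectory of change of the two continuous outcome variables (SSQ and Pharyngeal Compliance) within subjects", running from just after dilatation to 12 months. It adds: "These estimates will help to determine required sample size to show clinically relevant effect".

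The comparison that the full trial must make is given in Section 3. Treated patients are expected to "have a more compliant POJ, 12 months after endoscopic dilatation when compared with placebo treatment", and the secondary hypothesis is a lower dysphagia relapse rate than on placebo. Both are between-arm statements.

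Section 4.5 sets 40 participants, 20 per group. Section 8.1 says this number is "based on the number of patients we estimate to recruit over the course of 12 months and maintain the study within budget". Section 4.1 acknowledges that the pilot is not powered to prove efficacy. The protocol gives no minimum important difference, SD or precision target for either the SSQ or POJ compliance.

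**The concern.** There are two difficulties.

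First, a pilot with 20 per arm estimates a treatment effect very imprecisely. Required sample size varies with the inverse square of the effect, so ordinary sampling error in the estimate becomes a very large error in the planned size. The error is one-sided in its harm: the pilots that look most encouraging, and so are most likely to lead to a funded trial, are the ones that give too small a trial.

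Second, mean change within subjects after dilatation is not a treatment effect. It combines restenosis, any repeat dilatation and any drug effect. Section 2.2 itself reports 50% relapse at 19 months and 203 dilatations in 54 patients (203/54 ≈ 3.8 each), so the non-drug part could be substantial. Only the contrast with placebo isolates the drug.

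At stake is the adequacy of the later RCT, for which Section 8.2 says these estimates will be used in seeking funding. The conduct of the pilot and its participants are not affected.

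**Working it through.** **Inputs from the protocol.** 20 per arm (Section 4.5); 1:1 allocation (Section 7); 12-month comparison with placebo (Section 3). The 40 has no power calculation behind it, so there is no stated figure to reproduce beyond 2 × 20 = 40.

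**Assumptions, not in the protocol.** Two-sided 5% test and 80% power for the full trial; continuous outcome with SD = 1; true standardised effect d of 0.3, 0.5 or 0.8; the observed effect used unchanged in the sample-size formula.

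**1. Precision of the between-arm difference.**
Half-width = t(0.975, 38) × √(2/20) = 2.024 × 0.316 = 0.64 SD. With an assumed 20% loss (16 per arm) it is 0.72 SD.

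An observed d of 0.5 has a 95% interval of −0.13 to 1.13. The point estimate implies 63 per arm and the upper limit 13; the lower limit gives no defined size.

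**2. Consequence of sizing on the observed effect.**
n per arm = 2 × (1.960 + 0.842)² / d² = 15.70 / d², i.e. 175, 63 and 25 for d = 0.3, 0.5 and 0.8.

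The full trial is under-sized when the observed effect exceeds the true one. Its true power falls below 60% when the observed effect exceeds d × (1.960 + 0.842) / (1.960 + 0.253) = 1.266 d. Treat the observed effect as normal with standard error 0.316, and condition on its favouring active treatment (a positive pilot):

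| True d | P(positive) = Φ(d/0.316) | Under-sized: 0.5 / P(positive) | Power < 60%: [1 − Φ(0.266 d/0.316)] / P(positive) |
|---|---|---|---|
| 0.3 | 0.829 | 0.60 | 0.400/0.829 = 0.48 |
| 0.5 | 0.943 | 0.53 | 0.337/0.943 = 0.36 |
| 0.8 | 0.994 | 0.50 | 0.251/0.994 = 0.25 |

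Simulating pilots in which the SD is also estimated gives about 60%, 52% and 49% under-sized and 48%, 36% and 24% below 60% power. Results shift by up to about two percentage points with the normal or t version of the sizing formula.

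**3. What the same 40 patients can support.**
The 95% interval for the pooled SD on 38 degrees of freedom is 0.82 to 1.29 times the estimate, so planned size varies by a factor of 0.67 to 1.66. For a true effect of 0.5 (63 per arm needed), the 10th to 90th percentile of planned size per arm is:
- about 18 to 520 when sized on the observed effect;
- about 46 to 82 when the target difference is fixed at 0.5 and only the SD comes from the pilot.

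**4. Allowance for SD uncertainty.**
One-sided 80% upper limit: √(38 / χ²(0.20, 38)) = √(38 / 30.54) = 1.12. Sample size scales with its square, 38 / 30.54 = 1.24, i.e. 24% more. At 16 per arm the factors are 1.13 and 1.28.

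**The case against.** The strongest reply is that the protocol never says the observed effect will be inserted in a formula. Section 3 speaks of information from feasibility, time, cost and effect size together. Section 8.2 says the estimates will help size a trial for a clinically relevant effect, which can be read as taking the target from clinical judgement and the variability from the pilot. That reading is fair for Section 8.2, and it is why the percentages above are conditional. It does not dispose of Section 3, which names effect size outright, and no clinically relevant difference is stated for the pilot's SD to be set against.

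A reader might infer several stronger points that the documents do not support:
- *That the pilot's effect size is the wrong kind of quantity.* In a 1:1 placebo-controlled pilot it is a between-arm quantity; its weakness is imprecision. Only the within-subject change in Section 8.2 is not the treatment contrast.
- *That within-subject change has no use.* Its SD is a legitimate input for a trial analysed on change, and Section 8.2 also says that efficacy will be evaluated.
- *That 40 patients or the lack of power is an error.* Both are openly explained and acceptable in a pilot.
- *That sizing is the pilot's main purpose, or that a small observed effect would stop the programme.* Section 4.1 gives testing the design as the purpose, Section 8.2 lists eight feasibility measures, and there is no go/no-go rule on effect size.
- *That baseline or stratum adjustment is missing.* Section 7 stratifies by previous dilatation, but the analysis model commonly belongs to a SAP, which is not shown here.

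It can also be objected that reporting the between-arm difference promotes the quantity said to be poorly estimated. That is met by reporting it with its interval and keeping it out of the sizing.

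**Conclusion.** The point holds as a low-cost improvement. Section 3 makes the pilot effect size an input to the full trial's sample size, Section 8.2 points to within-subject change for the same purpose, and no between-arm target is named. The 0.64 SD half-width depends only on 20 evaluable patients per arm and a comparison of means. The under-sizing figures (about half to three-fifths of positive pilots, with a quarter to a half leaving true power below 60%) depend on direct use of the observed effect, true effects of 0.3 to 0.8 SD, a two-sided 5% test and 80% power. All of these are assumptions, and a sponsor who sized on clinical judgement would avoid the problem. The text as written does not commit the sponsor to that.

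**What to change.** In Sections 3 and 8.2:

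1. Remove effect size from the quantities used to predict the full trial's sample size.
2. State that the full RCT will be sized on a clinically important between-arm difference, specified with its rationale before the pilot data are unblinded.
3. State that the pilot supplies the outcome SD (including the SD of change), retention and adherence, with an allowance for uncertainty in the SD. A one-sided 80% upper limit (× 1.12) is one convention among several.
4. Report the 12-month between-arm difference with its 95% confidence interval as descriptive only, with no efficacy claim. Within-subject trajectories can be kept as description.

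The cost is wording, plus the work of agreeing on a target difference. Nothing changes in procedures, visits or pilot size. The downside falls on the next trial: with the 80% limit on the SD its planned size rises by about 24% (about 28% if only 16 per arm are evaluable).

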4 STUDY DESIGN

4.1 Approach

The study design mimics the design of a RCT however it is not powered to show unequivocal proof of treatment's efficacy. Its purpose is to test the design of the full-scale trial which then can be adjusted if problems are identified in the pilot study to improve the likelihood of a clear outcome later.

4.2 Design

Pilot double-blind randomised controlled trial

4.3 Study Groups

Patients with dysphagia symptoms undergoing dilatation for a stricture of a pharyngo-oesophageal junction.

Subjects will be randomised into 2 groups:

- 1) Receiving Pentoxifylline + Vite. E treatment
- 2) Receiving placebo

4.4 Treatment

- 1) Compounded tablets of Pentoxifylline and Vitamin E, three times a day for 12 weeks, combined daily dose of 1,200mg of Pentoxifylline and 1,000IU Vitamin E Succinate

Or

- 2) Identical placebo tablets

Active and placebo drugs will be supplied by STENLAKE compounding chemist.

4.5 Number of participants

40 participants (20 per group)

4.6 Number of centres

This is a single centre study (St George Hospital)

4.7 Duration

2 years from the time of ethics approval.

5 PARTICIPANT SELECTION

5.1 Inclusion criteria

- Age ≥ 18
- Completion of radiotherapy with or without adjuvant chemotherapy and dysphagia symptoms defined as Sydney Swallow Questionnaire > 234 (upper limit of normal).
- Clinical indication for endoscopic dilatation demonstrating a pharyngo-oesophageal junction stricture confirmed by EndoFLIP (see 6.3.2 below) defined as POJ compliance below the established lower limit of normal ($CSA < 4.0 \text{ mm}^2/\text{mmHg}$) [8].
- No Vitamin E supplementation at least 2 weeks* before commencement on study medication and willingness to abstain from Vitamin E supplements including multivitamin formulations containing Vitamin E for the duration of the study. * (Plasma half-life of alpha-tocopherol is $\sim 44\text{hrs}$)

5.2 Exclusion criteria

- Individuals who cannot provide informed consent due to any reason (language barrier, impaired cognitive function)
- Recurrence or persistent disease following head and neck cancer treatment.
- Pre-existing disorder known to cause pharyngeal dysphagia such as: MVA, MND, Parkinson's, inflammatory myopathy.
- Pre-existing oesophageal disease known to cause dysphagia such as eosinophilic oesophagitis, achalasia, oesophageal cancer.
- Either current pregnancy, intended pregnancy or breastfeeding during the study
- History of severe haemorrhage, e.g. massive retinal haemorrhage, cerebral haemorrhage, acute myocardial infarction or recent history of peptic ulcer.
- Concomitant or recent use of Warfarin or impaired blood clotting.
- Previous intolerance to Pentoxifylline or other methylxanthines such as caffeine, theophylline, and theobromine.
- Significant impairment of renal or hepatic function or other co-morbid conditions which in the opinion of the investigators preclude inclusion in the study

5.3 Clinician screening guideline

Refer to Screening Guideline v1.0 document to flag participants with increased risk of adverse events and drug interaction for close monitoring.

6 STUDY OUTLINE

6.1 Study Flow Chart

[figure not shown]

Figure 1. Study Flow Chart

6.2 Study Plan

Following informed consent, but prior to randomisation, participants will undergo a baseline diagnostic endoscopy as per 'standard of care'. While sedated the compliance (elasticity) of their pharynx will be assessed using EndoFLIP (see 6.3.2 below) and they will undergo an endoscopic dilatation procedure. If baseline compliance of the POJ is reduced ie: a fibrotic stricture is present, the EndoFLIP assessment will be repeated after dilatation and participants will be randomised to receive either 1) PTX + VitE or 2) Placebo after the dilatation. Endoscopy and dilatation is part of routine care and is indicated regardless whether a patient is participating in the study.

NOTE: In case when dilatation endpoint is not met during the first dilatation (see 6.3.3 below), endoscopy will be repeated until one of the endpoints is met and then post-dilatation EndoFLIP assessment will be performed and participant will be randomized and commence study medication. Repeated incremental dilatation are part of routine care (see 6.3.3 below).

Following discharge, patients will be followed-up by a monthly phone call while on study medication for 3 months (see telephone script in appendix). From 3 to 12 months participants will have the option to attend a 'Swallow clinic' every 3 months where they will return unused medication and their swallowing function will be assessed by SSQ. Otherwise medication and SSQs will be returned by posting ad reply-paid envelopes to the participants.

Repeat endoscopy with EndoFLIP will be performed at 12 months to assess the change in POJ compliance from the immediate post-dilatation assessment.

6.3 Component measurement techniques

6.3.1 Sydney Swallow Questionnaire (SSQ)

17 question self-reported inventory developed and validated by us [17] measuring the severity of oropharyngeal dysphagia. Importantly the SSQ has also been validated in the HNC patient population [18] and demonstrated to be a precise, reliable and valid tool to assess dysphagia severity [17]. SSQ assesses the physiologic aspects of swallow function, and yields a total severity score (range 0-1700; ULN <234 [7]).

6.3.2 Pharyngeal distensibility measurements

Endoluminal Functional Lumen Imaging Probe (EndoFLIP), an impedance planimetry based technique is a TGA Approved (ARTG: 173958) and validated measurement of pharyngeal strictures. Details about the unit and technique are provided in the appendix

6.3.3 Endoscopic dilatation of POJ

Endoscopic dilatation will be performed under conscious sedation. The upper gastrointestinal tract will be examined with a standard adult gastroscope (Ø 9.2 mm) or a pediatric gastroscope (Ø 5.4 mm) if the adult scope could not pass a stricture. Dilatations in all cases will be performed using Savary-Gilliard rigid dilators (Cook Medical, Bloomington, IN, USA) in the standard fashion over an endoscopically placed guide wire [19]. Sequential dilators will be passed with increasing diameters (1-mm increments) until either a mucosal tear is observed or significant resistance is encountered by the endoscopist.

Dilatation will be repeated every fortnight until either a passage of an 18-mm dilator or when the endoscopist feels it unsafe to proceed. Based on existing pilot data, a median of 3 dilatations per patient is required to achieve an outcome [20]. Hence, patients will be re-scheduled for repeat dilatation every 2 weeks until: a) 18mm dilator is passed, or b) further increase in size is deemed unsafe by the endoscopists.

